Candidacy for ED-initiated BUP will serve as the initial criteria for determining a patient's potential study eligibility, as well as for the denominator of the primary implementation outcome. This terminology differs from the terminology of "eligible and willing to receive ED-initiated BUP" used in the parent study for the aforementioned reasons and lessons learned through the parent study. In brief, any patient who would have met the eligibility criteria as defined in the parent study will be eligible in the ancillary study as will patients identified to have nonmedical opioid use without explicit documentation or evidence of contraindications to treatment. To be eligible for research participation, all criteria used to determine one's eligibility and willingness to receive ED-initiated BUP must be satisfied as confirmed through research staff assessments or sufficient EMR documentation. The eligibility criteria are discussed in greater detail in sections 7.2 and 7.3. The means of identifying candidates for ED-initiated BUP will include the medical record abstraction procedures used in CTN-0079. In addition, using methods adapted from CTN-0069, research staff will identify potential participants by assessing them directly via conducting health surveys. (Study entry procedures are discussed further in section 9.0.) The ED Health Survey has questions related to eligibility (for both ED-initiated BUP and study participation) embedded within general public health screening questions. Although this research assessment (the ED Health Survey) will be used primarily for recruitment purposes, all patients with OUD identified through this research assessment will be given an informational pamphlet. This minimal clinical intervention (health quiz and pamphlet) is unlikely to have a substantive effect on outcomes or to influence clinical procedures associated with the delivery of the ED-initiated BUP program. Importantly, research staff will not communicate responses to the ED Health Survey to clinical staff. The study purpose will be described as a study to evaluate outcomes among ED patients with OUD (section 12.0).

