7.2 Full Study Population Eligibility Criteria

7.2.1 Inclusion Criteria

1. 18 years of age or older
2. Be able to speak English sufficiently to understand study procedures
3. Be a potential candidate for ED-initiated BUP by meeting either of the following two criteria:

- a. Clinical determination: Clinical documentation indicating the patient is a willing and eligible candidate for ED-initiated BUP or for whom this can be reasonably inferred, including any patient who receives ED-initiated BUP (via direct administration, prescription, or direct referral/transfer to BUP provider within 24 hours of ED discharge).
- b. Research determination: Both a and b below must be true at the time of study enrollment:
 - a) Assessment conducted by an RA indicates that the patient- (all must be true):
 - i. has had nonmedical opioid use within the last 7 days,
 - ii. meets DSM-5 criteria for moderate or severe OUD,
 - iii. denies methadone use within 72 hours of ED visit registration,
 - iv. is not engaged in formal MOUD treatment,
 - v. is not prescribed opioids for chronic pain management,
 - vi. reports being interested or “not sure” if interested in receiving BUP as elicited on the ED Health Survey during the index ED visit.
 - b) Absence of clinical documentation associated with the ED visit indicating that the patient is not a candidate for ED-initiated BUP.

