- Operationally, ED-expedited BUP is a warm hand-off to a provider who can provide (dispense and/or/prescribe) BUP within 24 hours of discharge from the ED. To be included, there must be confirmation of this handoff, inclusive of clinical documentation in the EMR of medical decision making indicating that the patient is being handed off/referred for BUP treatment to a specific provider, clinic, or service with the capacity and availability to provide BUP within 24 hours of the patients' ED discharge. This could include a patient being given an appointment at a specific time and location, transfer to a provider, facility, or inpatient service directly from the ED, or through a pre-arranged follow-up mechanism in which a treating provider/facility has agreed to accept patients referred from the ED. Such agreements often exist to ensure access to urgent follow up care after ED discharge (for other medical problems and, more recently, OUD) as it may not be practical or possible to schedule appointments, particularly outside of traditional business hours. Neither confirmation of a completed appointment (i.e., patient shows up and is seen) nor receipt of BUP at the dedicated follow-up appointment will be required as privacy regulations may preclude our obtaining these data and as the patient and treating provider may elect to treat with alternative regimes (e.g., methadone, naltrexone).
- Candidate for ED-initiated BUP (denominator): In the parent study, the denominator included patients with clinical documentation of non-medical opioid use and documentation: (a) affirming eligibility and willingness to receive ED-initiated BUP (or for whom this could be reasonably be inferred) or (b) confirming receipt of BUP administered or prescribed as part of the ED visit. For the ancillary study, we will include all patients identified to have non-medical opioid use and exclude only those for whom there is documentation or other evidence of the patient *not* being eligible or willing to receive ED-initiated BUP (or for whom this could be reasonably be inferred). Rationale: The rationale for this change is that it should provide more complete capture (expect higher sensitivity and lower specificity) and hold the sites more accountable for ensuring

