complete clinical documentation. All patients identified to have non-medical opioid use will be assumed to be candidates for ED-initiated BUP unless there is documentation indicating otherwise. In this way, inadequate documentation would be more likely to dilute positive outcomes rather than strengthen them. This outcome is somewhat analogous to a metric used as a Centers for Medicare and Medicaid Services (CMS) accountability measure of quality for treatment of pneumonia in EDs – the proportion of patients who receive antibiotic treatment for pneumonia within 4 hours of ED triage. The denominator includes all patients with diagnosis of pneumonia and excludes only patients for whom specific documentation exists indicating why antibiotics were not administered within 4 hours (e.g., patient refused, atypical presentation delaying diagnosis, etc.).

- Patients may be identified as candidates for ED-initiated BUP through EMR abstraction and/or through RA assessments embedded in health surveys using methods adapted from CTN-0069. This represents a change from the parent study, which was limited to EMR abstraction. RAs will approach patients in the ED to conduct health surveys embedded with questions to screen for non-medical opioid use and, if positive, assess for the main criteria for establishing one's eligibility and willingness to receive ED-initiated BUP (i.e., untreated, moderate to severe OUD; opioid use within 7 days; absence of common contraindications; interest in BUP treatment – as per section 7.2). Specific criteria of how to reconcile discrepant EMR and RA obtained data will be outlined in the MOP. Rationale: This additional means of identifying patients who are potentially eligible for ED-initiated BUP (and subsequent enrollment) will allow us to identify the target population in the event of diminished fidelity to clinical screening for non-medical opioid use. Further, we will use these data for quality assurance of clinical screening and secondary clinical assessments.

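### Section 8.1.1 gives two incompatible exclusion rules for the primary reach denominator, and the rule that admits inference can weaken or reverse the claim that poor charting dilutes reach.

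*Combined protocol and SAP*

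**What the plan says.** Section 8.1.1 defines the denominator of the primary implementation outcome in one bullet, which contains two rules.

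- **Operational sentence.** The starting group is everyone found to use opioids non-medically, and the only exclusions are on evidence against candidacy. The clause that describes those excluded is put in the negative and reads "being eligible or willing to receive ED-initiated BUP (or for whom this could be reasonably be inferred". With the words that precede it, this gives three grounds for exclusion: documentation, other evidence, and reasonable inference.
- **Rationale.** "All patients identified to have non-medical opioid use will be assumed to be candidates for ED-initiated BUP unless there is documentation indicating otherwise". From this the plan concludes that "inadequate documentation would be more likely to dilute positive outcomes rather than strengthen them". It likens the measure to a pneumonia quality metric that "excludes only patients for whom specific documentation exists indicating why antibiotics were not administered within 4 hours".

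Section 5.3 words the rule a third way, admitting "patients identified to have nonmedical opioid use without explicit documentation or evidence of contraindications to treatment". It does not mention inference.

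Section 12.3.1 repeats the outcome definition but has no exclusion rule for the denominator. Section 8.1.1 leaves to the manual of operations only the reconciling of discrepant medical-record and research-assistant (RA) data. No section says what may support an inference, who makes it, or whether that person knows if BUP was given.

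**The concern.** Two abstractors following different sentences of the same bullet could classify the same untreated patient differently, and the result feeds straight into the primary estimate. Section 12.4 makes that estimate purely descriptive, a proportion with a 95% confidence interval, so the denominator rule is a large part of what the result means.

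The direction of error also matters. The plan defends its broad denominator on accountability grounds: incomplete charting should count against a site. That holds if only documentation can exclude. If an abstractor may also infer that an untreated patient was unwilling or ineligible, a partly charted patient can leave the denominator, and reach goes up.

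In the parent-study definition, which 8.1.1 restates just before its own rule, the inference clause widened inclusion. Placed after the word not, it widens exclusion. It may have been carried over without that effect being intended.

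**Working it through.** **1. The plan's own figures.** Sections 12.2 and 12.5 assume 300 candidates, about 100 per site, and true reach of 40% to 90%.
- Last row of Table 4: 300 × 0.40 = 120 and 300 × 0.90 = 270. Both reproduce.
- The 12.5.1 estimator averages three site values (S+1)/(n+2), with variance equal to the sum of site variances divided by 9. At 40% reach each site has α = 41 and β = 61, so its variance is 41×61/(102²×103) = 0.002334. Half-width = 1.96 × √(3×0.002334/9) = 0.055. At 90% (α = 91, β = 11) it is 0.035.
- In 10,000 simulated trials with equal sites and no site difference, the 90th percentile of interval width at N=300 was 0.110 at 40% reach and 0.075 at 90%. This agrees with the plan's statement of below 0.2.

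**2. Which patients an inferred exclusion can remove.** Section 7.2.1(3a) counts as a candidate, for enrollment, "including any patient who receives ED-initiated BUP (via direct administration, prescription, or direct referral/transfer to BUP provider within 24 hours of ED discharge". The parent denominator also counted patients who were given or prescribed BUP, and Section 2.1 says everyone who met the parent criteria is a candidate here. So inferred exclusions fall on untreated patients.

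**3. Wrongly inferred exclusions.** Let T be the number treated among 300 true candidates, and f the share of untreated true candidates wrongly inferred away. Then reach = T / [300 − f(300 − T)]. The values of f are assumptions.

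| f | True reach 40% (T=120) | True reach 90% (T=270) |
|---|---|---|
| 10% | 120/282 = 42.6% | 270/297 = 90.9% |
| 20% | 120/264 = 45.5% | 270/294 = 91.8% |
| 30% | 120/246 = 48.8% | 270/291 = 92.8% |

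The shift is +2.6 to +8.8 points at 40% reach and +0.9 to +2.8 points at 90%. At 40%, wrongly removing 36 of 180 untreated candidates moves the estimate by about one half-width. At 90%, the whole range stays inside the half-width.

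**4. If most inferences are right.** Suppose 18, 36 or 54 patients are excluded by inference but only a quarter of them are true candidates (assumed). The true candidates lost are 4.5, 9 and 13.5. Reach is 120/295.5 = 40.6%, 120/291 = 41.2% or 120/286.5 = 41.9%, a shift of +0.6 to +1.9 points.

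**5. Can the dilution property reverse?** Assume 120 treated and 180 untreated true candidates, 50 untreated non-candidates, and thin charts for 40% of the untreated in both groups. Fully charted non-candidates are excluded.
- Documentation only: the 20 thinly charted non-candidates stay in, giving 120/(300+20) = 37.5%. This is dilution, as the plan says.
- Inference removes a quarter of thin charts regardless of true status (18 candidates, 5 non-candidates): 120/297 = 40.4%.
- Inference removes half (36 and 10): 120/274 = 43.8%.
- Inference removes exactly the 20 non-candidates: 120/300 = 40.0%, which is correct.

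Reach overshoots when the true candidates wrongly removed outnumber the non-candidates left in.

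**The case against.** The strongest reply is that one-sidedness is not peculiar to inference. Any exclusion for ineligibility or unwillingness falls on untreated patients, including the explicit ones, and removing a true non-candidate corrects the denominator. This stands. The bias comes from mistaken inferences only, and step 3 supposes that all of them are mistaken. The 300 in Section 12.2 are also patients already taken to be candidates, so step 3 measures losses from that group and does not forecast the rule's overall effect.

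It can also be said that the wordings are closer than they look. Documentation that indicates otherwise need not state the reason outright, other evidence may mean RA survey answers, and Section 2.1 allows candidacy to be presumed from available data. The plan claims only that dilution is more likely, and calls the pneumonia metric only somewhat analogous. This softens the conflict without removing it: the inference clause stands apart from other evidence, and a metric that excludes on specific documentation does not admit inference.

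Finally, Sections 8.3 and 12.7 plan exploratory permutations of the denominator and tracking of how data were captured, and 9.2.3 collects patient-level data for quality assurance of abstraction. These could host the check, but none commits to separating explicit from inferred exclusions.

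A reader might infer that inflation will be greatest at the sites that chart least. The documents do not support that. A reasonable inference needs some basis, and a chart with no information leaves the patient in under either rule. The exposure lies in partly completed charts.

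**Conclusion.** The point holds: Section 8.1.1 gives two rules for the primary denominator, 5.3 adds a third wording, and nothing in the documents decides between them. The inference clause can weaken or reverse the dilution property that the plan relies on.

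The size cannot be determined. Step 3 (+2.6 to +8.8 points at 40% reach, +0.9 to +2.8 at 90%) applies if 10% to 30% of untreated true candidates are wrongly excluded. Step 4 (+0.6 to +1.9 points at 40%) applies if only a quarter of inferred exclusions are wrong. Both rest on assumed rates.

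A reader might go further and conclude that reach will be overstated. The documents support only that it can be, since accurate inference would bring the estimate nearer the truth.

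This is a should-fix point. The outcome is descriptive with no test, and the failed-sustainability rule in 5.5 and 12.9 compares patients treated per six months, so no decision in the trial depends on this denominator.

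**What to change.** - Reconcile the wordings in 5.3 and 8.1.1 into one exclusion rule and repeat it in 12.3.1.
- For the primary analysis, exclude only on a charted reason or an RA-recorded failure of a 7.2.1(3b) criterion. This follows the rationale in 8.1.1 and keeps RA answers as a legitimate source outside the chart.
- Add one abstraction field for the basis of each exclusion, explicit or inferred. Patients whose non-candidacy is only inferred stay in the primary denominator and are flagged.
- Report exclusion counts by basis and by site, with a sensitivity analysis of reach that also removes the inferred exclusions.

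The cost is a wording change, one field and one extra estimate. The field should be in place before abstraction starts, because recovering the basis later would mean reviewing charts again. The downside is that some true non-candidates stay in and reach is slightly lower. Section 8.1.1 already accepts this in expecting higher sensitivity at the price of specificity.

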9.4.1.1 Recruitment

Research staff will work rotating shifts in the ED, providing coverage on weekdays, evenings, and weekends. Shifts will be scheduled so that patients can be recruited on all days of the week. During recruitment shifts, research staff will approach ED patients in a prioritized order, such that patients who are most likely to be eligible will be approached first. For example, patients who present to the ED seeking treatment for OUD or who were identified through triage screening to have non-medical opioid use would be approached before other patients; prioritization procedures will be further described in the MOP. The integration of opioid screening into clinical care via CTN-0079 will facilitate pragmatic identification of potential participants.

Research staff will screen and assess ED patients for study eligibility using questions embedded in a health survey (ED Health Survey). We have successfully used the strategy of embedding substance use questions in a general health survey as a method to screen for drug and alcohol use.[16, 17] Embedded questions have also been noted by the World Health Organization to improve the reliability of self-reported behavior.

Upon approach, the RA will use an IRB-approved script to seek permission to complete the ED Health Survey. A Waiver of Documentation of Informed Consent will be requested to complete the ED Health Survey. The ED Health Survey will begin with introductory questions (e.g., patients' access to a primary care provider and transportation) followed by use of legal substances (tobacco, alcohol) prior to asking about opioid use. Patients endorsing non-medical opioid use will then be asked to provide verbal consent to answering a series of simple questions to assess whether they are likely candidates for ED-initiated BUP, including the DSM-5 checklist for OUD (see section 7.2) and, if so, additional questions to determine eligibility for study participation (e.g., prisoner status assessment).

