Patients who receive ED-initiated BUP during times without research staff coverage will be contacted for potential study participation as soon as possible following ED discharge. Candidates who do not receive BUP will not be contacted once they have left hospital premises. As in the parent study, research staff will utilize available contact information, including information provided at registration or documented in the EMR, to contact candidates, assess eligibility, and offer study participation. Each site's clinical protocol includes a procedure to notify ED patients that clinical or research staff may contact them for follow up purposes and/or to discuss participation in a research study. Patients may opt out of contact from research staff. Assessment of study eligibility will be conducted by trained research staff and may be completed by phone or in person (upon return). Candidates who are determined to be eligible for and interested in study participation will be scheduled for written consent and baseline assessments to be completed in person, ideally within 72 hours of ED discharge but recruitment efforts may continue for up to 7 days post ED discharge.

It is anticipated that some patients will be difficult to reach due to insufficient contact information, homelessness, admission to a treatment program, or other reasons. Of the patients reached, it is expected that some may choose not to participate and that some patients may fail to present for the baseline visit within the visit window. Research staff will make repeated attempts (at varying times of the day- morning, afternoon, evening) to contact all candidates utilizing multiple methods of communication (i.e., call, text, email). Research staff will also strive to reduce barriers to participation by offering to complete the visit at a time and location that is convenient for the participant. All candidates will be informed that they will receive compensation for participation.

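### Does adding survey-identified candidates to the reach denominator make the primary estimate depend on research-assistant coverage in a way the plan must correct?

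*Combined protocol and SAP*

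**What the plan says.** The primary implementation outcome is the proportion of candidates for ED-initiated buprenorphine (BUP) who receive it directly or by a warm handoff within 24 hours. It is pooled over the Post-IF and Maintenance Periods (Section 12.3.1).

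- **Who is in the denominator.** Section 8.1.1: "Patients may be identified as candidates for ED-initiated BUP through EMR abstraction and/or through RA assessments embedded in health surveys". Section 12.3.1 likewise allows both chart abstraction and research staff assessment as sources. Section 5.3 adds that "research staff will identify potential participants by assessing them directly via conducting health surveys".
- **Why the survey was added.** The parent study used chart abstraction alone. The stated reason for the second route is to "identify the target population in the event of diminished fidelity to clinical screening for non-medical opioid use".
- **Who is taken out.** Section 8.1.1 first says "we will include all patients identified to have non-medical opioid use and exclude only those for whom there is documentation or other evidence" that the patient is not eligible or willing. It then says patients with non-medical use are "assumed to be candidates for ED-initiated BUP unless there is documentation indicating otherwise". The same section leaves the rule for conflicting chart and survey data to the Manual of Operations.
- **How the survey is run.** "Research staff will work rotating shifts in the ED" (Section 9.4.1.1), approaching the patients most likely to be eligible first. "Candidates who do not receive BUP will not be contacted once they have left hospital premises". Appendix A (Recruitment Monitoring) lets recruitment reports inform shifts and staffing during enrolment.
- **What is analysed.** Section 12.4 makes the primary analysis descriptive, with a 95% confidence interval and no inferential test. Sections 4.4, 8.3 and 12.7 list alternative versions of reach, one of them limited to candidates identified through the chart. Section 8.3 commits to tracking the method of data capture for this purpose.

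**The concern.** Treated and untreated candidates are not found in the same way. Receipt of BUP is abstracted mainly from the health record, so a treated patient is normally counted whether or not an RA was on shift. An untreated patient whom clinical screening missed is counted only after an RA survey during the visit. Section 5.3 describes that survey in these terms: "Although this research assessment (the ED Health Survey) will be used primarily for recruitment purposes". Coverage is partial and can be changed during the study. More RA hours could add untreated candidates and lower reach; fewer could raise it.

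The opposite effect is also conceivable. If a survey answer counts as other evidence, it could remove an untreated patient whom the chart had identified, and so raise reach.

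At stake is how the single pooled figure is read in a study of sustainability. The confidence interval covers sampling error but not a shift in who was found. Two further points add to the worry. The chart-only version is exploratory, so it need not stand beside the primary result. And Section 9.2.2 says the chart-review dataset supplies the primary outcome, without mentioning survey-identified candidates.

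**Working it through.** **Inputs.** 300 candidates, spread evenly over three sites and two periods (Sections 12.2 and 12.5), so 100 per site and 150 per period. Assumed reach of 40% to 90% (Section 12.5). Estimator from Section 12.5.1. The number found by RAs alone is not given and has to be assumed.

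**The plan's own figures.** Table 4 reproduces: 300 × 0.40 = 120 and 300 × 0.90 = 270. A 10,000-run simulation of the Section 12.5.1 estimator gives largest 90th-percentile interval widths of 0.142, 0.124 and 0.111 at N = 180, 240 and 300. All are under the stated 0.2. The text does not define how the site effect enters; a logit shift of −Δ, 0, +Δ was assumed.

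**Half-width at N = 300.** With α = 100p + 1 and β = 100(1 − p) + 1, each site has v = αβ / [(α + β)²(α + β + 1)], and h = 1.96 × √(3v/9).
- p = 0.4 or 0.6: v = 41 × 61 / (102² × 103) = 0.002334, h = 0.0547.
- p = 0.9: v = 91 × 11 / (102² × 103) = 0.000934, h = 0.0346.

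**Effect of RA-only candidates.** Let k of the 300 be RA-only and all untreated, with chart-only reach p. Primary reach is p(300 − k)/300, so the shift is pk/300. Setting this equal to h gives k = 300h/p:
- p = 0.4: 41.0, about 41 patients (14% of 300)
- p = 0.6: 27.3, about 28 patients (9%)
- p = 0.9: 11.5, about 12 patients (4%)

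If the half-width is taken at the lowered reach instead, the counts are 40, 28 and 14. For k = 10 the shift is 0.4 × 10/300 = 1.3 points, 0.6 × 10/300 = 2.0 points and 0.9 × 10/300 = 3.0 points, below the half-width each time.

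**Across periods.** Take chart-only reach of 60%, with 10 RA-only candidates in one period and 30 in the other. Reach is 0.6 × 140/150 = 56% against 0.6 × 120/150 = 48%. The half-width for the difference is 1.96 × √(0.56 × 0.44/150 + 0.48 × 0.52/150) = 0.113. The 8-point gap lies inside it.

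**What the survey route protects against.** Suppose 180 of 300 true candidates are treated (60%) and clinical screening misses 28 untreated ones. Chart-only reach is 180/272 = 66%. The programme would look better because it screened worse. Counting RA-found patients corrects part of that error.

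**The passages side by side.** Section 9.2.2 describes review of charts of patients screening positive for opioid use. It does not restrict this to clinical screening, so it is silent on survey identification and does not contradict Section 12.3.1. The two wordings in Section 8.1.1 on removal differ, but that section assigns conflicts between sources to the Manual of Operations. Section 7.2.1 requires both a positive RA assessment and no contrary clinical documentation for a research determination, so the two sources are not left wholly unordered. The interim rule (Sections 5.5 and 12.9), the comparison of provision rates and the diffusion curves (Section 4.2) use counts over time, so this denominator does not touch them.

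**The case for a change.** The best case for a change is that a descriptive study has only its estimate to offer, so the reader should see how much of it rests on a recruitment activity. Chart-only reach shows the net effect of the survey, and additions and removals could cancel within it. A table of candidates by source would show both. It should need no new data, because capture method is already tracked.

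Much of this stands as good reporting practice. The pooled figure does depend on the RA route to an unknown extent, and such a table would help. But it would leave the denominator, estimator, sample size and every decision rule as they are. Moving chart-only reach from the exploratory section to sit beside the primary result alters neither number, and with no primary test there is no error rate to protect.

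Source counts would not isolate RA staffing either. RA-only candidates become more frequent when coverage rises and also when clinical screening lapses. Separating the two needs the number surveyed and the proportion screened clinically. Appendix A already monitors numbers screened by site and by RA, and Sections 8.2 and 12.3.3.2 already plan the proportion screened at triage.

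The harm by site or period is also loosely anchored. Primary and key secondary reach are pooled over periods. No section states that the reach proportion will be reported by site, and the comparison across all study periods is tertiary and limited to comparable data.

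**Conclusion.** No change to the plan follows. The dependence on RA coverage is genuine but is the price of a sensible choice: a chart-only denominator would reward a site for failing to screen. The sponsor saw the issue, gave a reason for the survey route, and planned both the tracking and the chart-only version that let a reader see its effect.

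The size is unknown. Shifts of one half-width (5.5, 5.5 and 3.5 points at 40%, 60% and 90%) need about 41, 28 and 12 RA-only candidates of 300, all untreated; ten would move reach by 1.3 to 3.0 points. These figures assume equal sites, ignore the slight shrinkage in the site estimates, and take zero receipt among RA-only candidates, which is the extreme case. The approach order in Section 9.4.1.1 may keep the RA-only group small, since patients seeking treatment or positive at triage are approached first and are probably already in the chart.

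The differing phrases on removal in Section 8.1.1 and the silence in Section 9.2.2 are drafting matters. The first falls to the reconciliation rule assigned to the Manual of Operations, which was not among the documents available. Analysts with capture method in the dataset can tabulate candidates by source when reporting, without an amendment.
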